## 11 SAFETY ANALYSES

### 11.1 EXTENT OF EXPOSURE

Study drug exposure will be listed, including subject number, previous study, concomitant medication use, BID to three times daily (TID) transition, exposure (weeks), and categorical exposure (by visit). Exposure is calculated as the time exposed to active study drug. For subjects treated with active drug during the parent study, exposure calculations will include their exposure during the parent study. For subjects treated with placebo during the parent study, exposure calculations will include only the exposure to active drug during the OL study. The summary of disposition and study drug exposure will detail the number (percent) of subjects who died during the study, as well as the study drug exposure both by categorical visits ( $\geq 3$  months,  $\geq 6$  months, etc.) and using descriptive statistics. The total study drug exposure (pt-years) will also be displayed.

Study drug dosing will be summarized at each visit by previous study and overall. The summary will include a categorical summary of current status (in study, death, progression of PAH, AE, consent withdrawn, lost to follow-up, discontinued for other reasons, etc.) and study drug dose (<1 mg, 1-<2.5 mg, 2.5-<5 mg, 5-<10 mg, 10-<20 mg, 20-<30 mg BID/TID), as well as a descriptive statistics summary of study drug dose (mg BID/TID).

Study drug dosing will also be summarized at each visit by PAH background medication use, grouping subjects into monotherapy and combination therapy groups. The summary table will mimic that presented in the summary of study drug dosing by previous study, but will produce a separate summary table for each PAH background medication use group.

The summary of BID to TID transition will detail the number (percent) of subjects who completed this transition and who had to transition back to BID (if applicable), and descriptive statistics on the doses both before and after the transition by previous study and overall. All of these summaries will be provided by previous study and overall.

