1.4 Clinical Hypothesis

This open-label study will evaluate the safety of continued therapy with UT-15C SR in subjects who completed assessments in Protocol TDE-PH-202, TDE-PH-203, TDE-PH-205, TDE-PH-301, TDE-PH-302, TDE-PH-308, or any other study evaluating UT-15C SR in patients with PAH. The study will also provide information about long-term dosing patterns. Finally, a 6-Minute Walk Test with Borg Dyspnea Score to be conducted after subjects have completed one year of treatment with UT-15C SR will provide information about the efficacy of long-term treatment.

With Amendment 5, subjects will have the option of modifying their dosing regimen from BID to TID. The intention of the dosing modification from BID to TID is to deliver a more sustained plasma concentration of treprostinil thereby providing systemic exposure to drug that resembles the approved parenteral product, Remodulin, while reducing the occurrence and/or severity of prostacyclin-related adverse events previously associated with the twice daily regimen.

The transition from BID to TID dosing should be made at the discretion of the investigator taking into account the subjects current disease state and tolerability of UT-15C.

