6.1.1 Twice Daily Dosing Regimen

The next dose of study drug should be taken the following morning. At this time oral dosing of UT-15C SR will be initiated at 0.25 mg twice daily (every 12 hours +/- 1 hour) immediately following (~10 minutes) breakfast and dinner. Subjects must be instructed to take the appropriate amount of 0.25, 0.5, 1, and/or 2.5 mg tablets based upon their given dose. In general, the dose of study drug should be increased in 0.25 to 0.5 mg increments every 3 days, in the absence of dose-limiting drug-related side effects, to ensure the subject receives the optimum clinical dose throughout the study. The 0.125 mg strength, if available, may be used throughout the study if a 0.25 mg dose increase is not tolerated and an intermediate dose is required. Dose changes should be conducted under appropriate medical supervision in consultation with the study site.

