10 DATA MANGEMENT AND STATISTICS

Completed CRFs will be forwarded to United Therapeutics or its designee for processing. A quality-assured computerized database will be constructed. Data will be listed and also will be summarized either in tabular and/or graphical presentations.

The safety of UT-15C SR will be assessed using laboratory assessments and reports of adverse events. All reported adverse events will be assigned MedDRA terms which will be listed and summarized according to intensity, seriousness and causality.

Efficacy assessments (6-Minute Walk/Borg Dyspnea Score) may be compared to assessments in Protocols TDE-PH-202, TDE-PH-203, TDE-PH-205, TDE-PH-301, TDE-PH-302, TDE-PH-308, or TDE-PH-304, as appropriate. Doses of UT-15C SR will be listed, summarized and analyzed for trends over time.

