## **8 GENERAL CONSIDERATIONS FOR DATA ANALYSES**

All available data for subjects enrolled in TDE-PH-304 (regardless of treatment with active drug) will be included in each soft lock and will be listed. All available data for enrolled subjects who were treated with active drug in study TDE-PH-304 will be summarized, as detailed in this SAP. Subjects from the 200 series studies (TDE-PH-202, TDE-PH-203, and TDE-PH-205) that enrolled into the TDE-PH-304 study will be pooled for summarization purposes with the two de novo subjects previously enrolled in the TDE-PH-301 study. These two de novo subjects were initially enrolled in TDE-PH-301, but were later withdrawn from that study following a temporary drug recall in June 2006 and were subsequently directly enrolled in the TDE-PH-304 OL study. Likewise, subjects from studies TDE-PH-301 and TDE-PH-308 will be pooled for summarization purposes.

In general, listings will be sorted by subject number and scheduled assessment (if applicable). Listings will include assessment date, assessment time (if available), and study day. For data collected on a fixed schedule, the assessment identifier will also be included on the listing.

In general, the data will be summarized by scheduled assessment (if applicable). For continuous variables, the summary statistics will include the mean, standard deviation, standard error, median, lower quartile, upper quartile, minimum, and maximum. Minimums and maximums will be expressed using the level of precision in which the variable was collected. All other statistics will be rounded, using an additional decimal point. For discrete variables, summaries will include the frequency and percent in each category. Percentages will be rounded to a whole number. Whenever practical, categories of discrete variables will be ordered and labeled as they appear in the case report form (CRF), and all categories represented on the CRF will be included in summaries, even when they do not apply to any subjects in the study.

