### **8.2 PREMATURE DISCONTINUATION AND MISSING DATA**

A subject may voluntarily withdraw or be withdrawn from the study by the Investigator at any time for reasons including, but not limited to, the following:

- The subject wishes to withdraw from further participation.
- A serious or life-threatening AE occurs or the Investigator considers that it is necessary to discontinue study drug to protect the safety of the subject.
- The subject deviated from the protocol.
- The subject's behavior is likely to undermine the validity of his/her results.
- The subject becomes pregnant

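### By-visit dose summaries alone cannot separate titration from changes in who remains, and the direction of any distortion is unknown

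*SAP*

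**What the plan says.** The protocol presents dose over time as something the study will deliver. Section 1.4 states: "The study will also provide information about long-term dosing patterns". Section 10 states: "Doses of UT-15C SR will be listed, summarized and analyzed for trends over time". It names no method.

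SAP 11.1 supplies the analysis: "Study drug dosing will be summarized at each visit by previous study and overall". At each visit the table gives subject status, dose bands, and descriptive statistics of dose. The status rows are described as follows: "The summary will include a categorical summary of current status (in study, death, progression of PAH, AE, consent withdrawn", with further categories after that. The dose statistic is described as "as well as a descriptive statistics summary of study drug dose (mg BID/TID". Table 14.1.6.1 gives this by previous study and overall, and Table 14.1.6.2 by PAH background medication. Table 14.1.6.3 gives doses before and after a BID-to-TID transition. It is the only planned summary that compares a subject's dose with that subject's own earlier dose.

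SAP section 8 sets the data base: "All available data for enrolled subjects who were treated with active drug in study TDE-PH-304 will be summarized, as detailed in this SAP". SAP 8.2, whose title covers premature discontinuation and missing data, lists reasons for withdrawal and stops there. It gives no rule for dose after a subject leaves. SAP section 5 allows interim analyses as often as yearly.

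**The concern.** Each by-visit mean is computed on a different set of subjects. If leaving the study is related to dose, the mean changes between visits because the set changes, even when no individual's dose does. Follow-up that is incomplete at an interim cut changes the set in the same way.

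Dose is also reported in mg BID/TID, which reads most naturally as the dose per administration. A subject who moves from BID to TID then shows a drop on that scale larger than the drop in total daily dose.

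At stake is the one statement the protocol promises about dose: whether it changes over long-term treatment. A moving by-visit mean could be taken as continued titration or its absence. The planned tables cannot tell these apart from a change in who is being averaged.

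**Working it through.** **Plan's own figures.** The documents give no dose mean, dropout rate or trend result, so there is nothing to reproduce. Every dose distribution and exit rate below is an assumption. The calculation shows how large the effect can be and which way it can go; it does not predict this study.

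**Main illustration.** Doses are lognormal with median 3.5 mg and log-SD 0.8, and each subject's dose never changes. Exit is exponential, with a yearly hazard h that depends on dose tertile.

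1. Overall mean = 3.5 × exp(0.8²/2) = 4.82 mg.
2. Tertile mean = 3 × 4.82 × [Φ(b − 0.8) − Φ(a − 0.8)], where a and b are the tertile limits on the standard normal scale (cut points ±0.431). This gives 1.58, 3.57 and 9.31 mg.
3. Share of each tertile still in study at 3 years: w = exp(−3h).
4. Mean among those remaining = Σ(w × tertile mean) / Σw.

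For hazards 0.30/0.20/0.10 from lowest to highest tertile, w = 0.407, 0.549, 0.741. The mean is (0.642 + 1.958 + 6.899) / 1.696 = 5.60 mg, and 5.60/4.82 = 1.16.

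For hazards 0.10/0.20/0.30 the weights reverse. The mean is (1.170 + 1.958 + 3.786) / 1.696 = 4.08 mg, and 4.08/4.82 = 0.85.

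| Yearly hazards, low/mid/high tertile | Mean at Month 36 | Change in mean | Change in median | Within-subject change |
|---|---|---|---|---|
| 0.40/0.20/0.10 | 5.87 mg | +22% | +31% | 0 |
| 0.30/0.20/0.10 | 5.60 mg | +16% | +23% | 0 |
| 0.25/0.20/0.15 | 5.21 mg | +8% | +11% | 0 |
| 0.20/0.20/0.20 | 4.82 mg | 0% | 0% | 0 |
| 0.15/0.20/0.25 | 4.44 mg | -8% | -10% | 0 |
| 0.10/0.20/0.30 | 4.08 mg | -15% | -19% | 0 |

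**Cross-check with a simpler model.** Half the subjects take 2 mg and half 6 mg, so the starting mean is 4.00 mg. The mean at year 3 is [2(1−d₁)³ + 6(1−d₂)³] / [(1−d₁)³ + (1−d₂)³], where d₁ and d₂ are the annual dropout in the low- and high-dose halves.

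- Equal 20% dropout: 4.00 mg, no change.
- 30% low, 15% high: (0.686 + 3.685) / (0.343 + 0.614) = 4.57 mg, +14%.
- 15% low, 30% high: 3.43 mg, -14%.

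**Regimen change.** These figures come from Protocol Table 6-1. Moving from 6 mg BID to 3 mg TID takes the per-administration dose to 3/6 = 50% and the total daily dose to 9/12 = 75%. Across the eight examples the per-administration ratio runs from 48.8% to 50%, and the total daily ratio from 73.2% to 75%. Suppose, as an assumption, that 30% of those remaining had transitioned by Month 36, independently of dose. The +16% becomes 1.16 × (0.70 + 0.30 × 0.50) = 0.99, about -1%. On this scale a regimen effect can cancel or reverse a dropout effect.

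**The case against.** **A reader might infer that mean dose will rise because low-dose subjects drop out.** The documents do not support that. Neither gives exit by dose. Protocol 6.1.1 limits dose increases by drug-related side effects, which makes exit at low doses plausible. But the protocol summary and section 6.1 also tie dose changes to PAH signs and symptoms, and section 3.3.2.3 ends participation when chronic parenteral prostanoid is added for worsening PAH. Subjects titrated up while deteriorating, who then leave, would pull the mean down. Nor do subjects who have not yet reached later visits push the mean upward, unless they take lower doses, and nothing says they do.

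**Attrition is not hidden.** The same table shows status by reason at every visit, Kaplan-Meier curves of discontinuation are planned, and Listing 16.2.5 gives individual dosing. This stands in part. A reader can see how many left and why. But status is not linked to last dose in any planned summary, and a listing does not replace a summary.

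**Dose is a secondary matter.** It is not among the objectives or endpoints, the SAP plans no test or model of dose, and by-visit description is conventional in an open-label extension. This also stands, and it limits how serious the point is. It does not remove the gap between a trend analysis promised in Protocol section 10 and a SAP with no summary suited to it.

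**Within-subject change could itself mislead.** If computed on the mg BID/TID scale, it would show a fall of about 50% at transition when total daily dose falls by about 25%. This is correct, and the fix therefore uses total daily dose.

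**Conclusion.** The point holds as a limitation of interpretation. The planned by-visit dose tables cannot distinguish titration from selective dropout, incomplete follow-up at interim cuts, or BID-to-TID transition, and no other planned summary fills that gap. The sign of the distortion is unknown. Under the main assumptions the Month 36 mean moves by about +16%, 0% or -15% with every dose held constant, depending only on how exit relates to dose.

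This rests on two things. The first is reading the denominator as subjects in study with a recorded dose, which the SAP implies but does not state. The second is the set of assumed doses and hazards, which fixes the size of the illustration but not the mechanism. If exit and incomplete follow-up are unrelated to dose, composition adds no drift and only the regimen effect remains. Acting on it is desirable rather than essential.

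**What to change.** In SAP 11.1 and Tables 14.1.6.1 and 14.1.6.2:

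- State the denominator for the dose statistics at each visit.
- Add within-subject change in total daily dose, between consecutive visits and from Month 12, for subjects with both values.
- Show the total daily dose path separately for subjects who reach Month 12, Month 24 and Month 36.
- Base any statement about dose trend on these rows, and keep the by-visit tables as a description of dosing among those present.

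Protocol 6.1 already has the dose recorded on the CRF at each study visit, and 6.1.2 has dose changes recorded there too, so no new data are needed. The cost is a longer table. The added rows remove the effect of changing composition, but they still describe only subjects who stayed long enough to contribute, and the text should say so.

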1.2.2 UT-15C SR Clinical Pharmacology

In solution, both treprostinil sodium and treprostinil diethanolamine are disassociated from their respective salt counter-ions and exist as the freely ionized form of treprostinil. As a result, the bioactive form present in the bloodstream is identical irrespective of the selection of the counter-ion. Given this premise, the development of this new diethanolamine salt of treprostinil is expected to retain the bioactivity and safety profile of treprostinil sodium.

The most frequent AEs associated with Remodulin in clinical trials of patients with PAH were related to the pharmacological properties of Remodulin and were generally not serious. These prostacyclin-related AEs included diarrhea, headache, and nausea. Remodulin has not been associated with any significant changes in laboratory parameters or end-organ toxicity. The safety profile noted in the open label extension study, with much longer durations of exposure and a larger, more diverse patient population, was consistent with the profile noted in the controlled trials. To date, well over 10,000 subjects and patients have been exposed to Remodulin. This number includes patients who have received single administration, to patients receiving continuous infusion for greater than 10 years.

[figure not shown]
UT-15C has been administered to approximately 1,600 subjects in phase I-III clinical trials. UT-15C doses of up to 3 mg twice daily (BID) have been administered to healthy volunteers and patients with PAH have received up to 22 mg BID in the ongoing phase III development program. The longest individual exposure is now greater than five years.

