6.1.2 Transition from Twice to Three Times daily Dosing

For subjects enrolled in the TDE-PH-304 study who are receiving UT-15C twice daily, dosing frequency may be transitioned from BID to TID. For applicable subjects, it is recommended to reduce the total daily dose administered during BID dosing by approximately 25% and divide the total daily dose into a TID regimen using the appropriate tablet strength(s). Please see Table 6-1 below for examples of transitioning from BID dosing to TID dosing. However, dose modification should occur in accordance with investigator judgment.

Table 6-1 Example Transition from Twice Daily to Three Times Daily Dosing of UT-15C

BID Dosing Regimen	Total Daily Dose with BID Dosing	Total Daily Dose with BID Dosing Reduced by 25%	TID Dosing Regimen	Total Daily Dose with TID Dosing
3 mg BID	6 mg	4.5 mg	1.5 mg TID	4.5 mg
5 mg qAM; 5.25 mg qPM	10.25 mg	7.6875 mg	2.5 mg TID	7.5 mg
6 mg BID	12 mg	9 mg	3 mg TID	9 mg
6.5 mg qAM; 6.625 mg qPM	13.125 mg	9.844 mg	3.25 mg TID	9.75 mg
10 mg BID	20 mg	15 mg	5 mg TID	15 mg
11 mg qAM; 11.5 mg qPM	22.5 mg	16.875 mg	5.5 mg TID	16.5 mg
13 mg BID	26 mg	19.5 mg	6.5 mg TID	19.5 mg
17.125 mg qAM; 17.25 mg qPM	34.375 mg	25.781 mg	8.5 mg TID	25.5 mg

Dose changes should be conducted under appropriate medical supervision in consultation with the study site. If dose titration is considered appropriate, site personnel will instruct the subject to modify their dose; dose changes will be recorded in source documentation and CRF by site personnel.

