6.1.3 Three Times (TID) Daily Dosing Regimen

For subjects entering the TDE-PH-304 study receiving a TID dosing regimen (e.g. TDE-PH-205), or for those subjects transitioning from BID to TID dosing, the dosing regimen should be managed as follows:

- TID (every 6-8 hours) with food
- Increases should occur in increments of 0.125 or 0.25 mg TID every 3 days.

In general, the dose of study drug should be increased in 0.125 to 0.25 mg increments every 3 days, in the absence of dose-limiting drug-related side effects, to ensure the subject receives the optimum clinical dose throughout the study. The 0.125 mg strength, if available, may be used throughout the study if a

0.25 mg dose increase is not tolerated and an intermediate dose is required. Dose changes should be conducted under appropriate medical supervision in consultation with the study site.

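### By-visit dose tables put BID and TID on one apparently per-dose scale, so a switch at the recommended 25% daily cut reads as about 50%, and one with daily dose unchanged as 33%

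*SAP*

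**What the plan says.** SAP 11.1 plans a dose table at each visit, by previous study and overall (Table 14.1.6.1). It has six bands (<1, 1-<2.5, 2.5-<5, 5-<10, 10-<20 and 20-<30 mg, labelled BID/TID), "as well as a descriptive statistics summary of study drug dose (mg BID/TID"). A second version by PAH background medication (Table 14.1.6.2) has the same layout: "The summary table will mimic that presented in the summary of study drug dosing by previous study". Neither is split by regimen, and neither gives mg/day.

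A separate BID-to-TID table (14.1.6.3) reports how many subjects switched or reverted, with "descriptive statistics on the doses both before and after the transition by previous study and overall". No unit is stated for those doses. The exposure listing also flags the transition.

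Two features of the protocol put both regimens into these tables:

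- **Switching during the study.** Amendment 5 lets subjects move from BID to TID. In Protocol 6.1.2, "it is recommended to reduce the total daily dose administered during BID dosing by approximately 25" per cent, but "dose modification should occur in accordance with investigator judgment".
- **Entry on TID.** Protocol 6.1.3 makes provision "For subjects entering the TDE-PH-304 study receiving a TID dosing regimen (e.g. TDE-PH-205"), and Protocol 6.1 has subjects on active drug keep their dose and regimen at entry. SAP 8 then combines the studies: "Subjects from the 200 series studies (TDE-PH-202, TDE-PH-203, and TDE-PH-205) that enrolled into the TDE-PH-304 study will be pooled for summarization purposes".

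**The concern.** A per-administration dose measures amount of drug consistently only while the number of administrations per day is fixed. Once BID and TID share a column, the same number means two daily doses, and the bands no longer rank subjects by daily dose.

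Protocol 1.4 says the study will inform on dosing over the long term, and Protocol 10 commits to examining doses over time. Switching happens during follow-up, so the change of unit enters the visit-to-visit comparison and can look like dose reduction. Subjects entering on TID from TDE-PH-205 also mix the units in the pooled 200-series column and the overall column. SAP 5 allows interim outputs as often as yearly and for regulatory submissions, so the tables would be produced repeatedly.

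**Working it through.** **1. Which scale is it?** The top band ends below 30 mg. Protocol 1.2.2 reports that "patients with PAH have received up to 22 mg BID in the ongoing phase III development program". Per administration, 22 mg fits 20-<30. Per day it is 2 × 22 = 44 mg, which fits no band. The last row of Table 6-1 (34.375 mg/day) would not fit either. The label and the bands therefore point to a per-dose scale, although the SAP never says so.

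**2. Reproducing Table 6-1.** All eight rows reproduce: BID daily total = AM + PM; reduced total = 0.75 × daily, to rounding; TID daily total = 3 × TID dose.

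**3. Change on each scale.** Per-dose change = TID dose ÷ mean of AM and PM dose − 1. Daily change = TID daily ÷ BID daily − 1. Four rows have unequal AM and PM doses and so no single BID value. Averaging them is my assumption.

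| Mean BID dose (mg) | TID dose (mg) | Per-dose change | Daily dose (mg) | Daily change | Band before → after | TID dose if daily unchanged (mg) |
|---|---|---|---|---|---|---|
| 3 | 1.5 | −50.0% | 6 → 4.5 | −25.0% | 2.5-<5 → 1-<2.5 | 2.00 |
| 5.125 | 2.5 | −51.2% | 10.25 → 7.5 | −26.8% | 5-<10 → 2.5-<5 | 3.42 |
| 6 | 3 | −50.0% | 12 → 9 | −25.0% | 5-<10 → 2.5-<5 | 4.00 |
| 6.5625 | 3.25 | −50.5% | 13.125 → 9.75 | −25.7% | 5-<10 → 2.5-<5 | 4.38 |
| 10 | 5 | −50.0% | 20 → 15 | −25.0% | 10-<20 → 5-<10 | 6.67 |
| 11.25 | 5.5 | −51.1% | 22.5 → 16.5 | −26.7% | 10-<20 → 5-<10 | 7.50 |
| 13 | 6.5 | −50.0% | 26 → 19.5 | −25.0% | 10-<20 → 5-<10 | 8.67 |
| 17.1875 | 8.5 | −50.5% | 34.375 → 25.5 | −25.8% | 10-<20 → 5-<10 | 11.46 |

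All 8 drop one band. The last column is BID daily total ÷ 3, a per-dose fall of 33.3%. On it 7 of 8 drop a band; 11.46 mg stays in 10-<20.

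**4. General rule.** For a daily cut c, apparent per-dose change = (2/3)(1 − c) − 1. The protocol recommends about 25% but leaves the reduction to the investigator, so the other values of c are assumptions:

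- c = 0: −33.3%
- c = 10%: (2/3)(0.90) − 1 = −40%
- c = 25%: (2/3)(0.75) − 1 = −50%
- c = 40%: (2/3)(0.60) − 1 = −60%

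For the per-dose value to read as unchanged after a switch, daily dose must rise from 2b to 3b, that is by 50%.

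**5. Loss of order.** The 5-<10 band covers 10-<20 mg/day on BID and 15-<30 mg/day on TID. A subject on 9.5 mg TID (28.5 mg/day) sits one band below a subject on 10 mg BID (20 mg/day).

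**6. Group level, illustration only.** The documents give no switching rate. Assume equal doses before the switch and a 25% daily cut. If 10%, 25% or 50% of subjects switch, the visit mean falls 5%, 12.5% or 25% per dose, against 2.5%, 6.25% or 12.5% in daily dose.

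**The case against.** - **The scale and the pooling are inferred.** The slash might mean that each dose is shown with its regimen, and no table shell is available to settle it. This stands as a limit on certainty, but the plan needs a change either way. If the scale is daily, the label is wrong and the bands are too short. If the regimens are to be kept apart, the SAP has to say so.
- **The 50% includes a real reduction.** This stands. At the recommended cut the daily dose does fall by a quarter; the artefact is the extra factor of 2/3, seen alone in the 33% case.
- **The percentages describe individual switchers, whereas the tables are group summaries.** This stands too. Switching is optional, and its frequency could be small or large.
- **The band counts depend on the examples.** This is true of 7 of 8: with daily dose unchanged, subjects on 3.75-<5, 7.5-<10 or 15-<20 mg BID would stay in band. It should not be read as a rate.
- **Table 14.1.6.3 and the listings already identify switchers.** They do, but they do not correct the by-visit tables, and the transition doses have no stated unit.
- **Per-dose figures are the protocol's own convention for prescribing and titration.** That justifies keeping them within regimen. Across regimens, Table 6-1 itself converts through total daily dose.
- **The consequence is modest.** The outputs are descriptive, no endpoint or decision rule uses them, and the SAP specifies no formal trend analysis. But description is what this open-label study will report about dosing.

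**Conclusion.** The concern holds. On the per-dose reading, which the bands support, the by-visit tables combine values that are not comparable. A switch at the recommended cut appears as a fall of about 50% when daily dose falls about 25%, and a switch with daily dose unchanged appears as a fall of 33.3%. These per-subject figures follow from arithmetic, given that reading and, for unequal AM and PM doses, averaging. The distortion of any visit mean or band percentage is not established, because it depends on the share of subjects on TID and on the reductions investigators choose. The flaw merits correction because dosing over time is something the protocol says it will describe; it does not threaten an endpoint.

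The 6MWD dosing quartiles and tertiles in SAP 10.1 are a lesser matter. Their dose scale is unstated, so they need a defined unit, but nothing shows that they use the mixed variable. TDE-PH-205 is already excluded from the walk summaries, and subjects past Month 12 when TID became available could not have switched before that walk.

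**What to change.** In SAP 11.1:

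- Make total daily dose (mg/day) the variable for Tables 14.1.6.1 and 14.1.6.2 and for any description of dose over time. Re-scale the bands to cover the daily doses in use; they must at least hold 44 mg/day.
- Show BID and TID separately beside the combined column, with the number of subjects on each regimen at each visit. Keep per-dose values within regimen only.
- State mg/day as the unit in Table 14.1.6.3.

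In SAP 10.1, state mg/day as the unit for the dosing quartiles and tertiles.

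The cost is SAP wording and revised table shells. Protocol 6.1 has the dose recorded on the CRF at each visit, Protocol 6.1.2 has dose changes recorded there, and the exposure listing already carries the transition. The CRF itself is not among the documents, so it is an assumption that unequal morning and evening doses can be summed from it. Readers used to per-dose figures will need the within-regimen rows. The change concerns reporting only and takes no view on the dosing rules.
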